2.3.2 Major Secondary Endpoints

The primary analysis for these two powered secondary endpoints will be based on the analysis applied to the time from randomization estimate. Sensitivity analyses will be performed on the time from procedure estimate. There are two major powered secondary endpoints:

- Composite measure of all-cause mortality, MI or stroke (mRS≥1 and increase by ≥1 from baseline) presented as a Kaplan Meier rate defined from randomization to 30 days post randomization This is the same as the primary endpoint measured at 30 days. Two sets of analyses will be performed. Days from the randomization date or procedure date to the first occurrence of the one of the events within this composite, an early withdrawal date, or the last follow-up date will be calculated for each patient respectively. For patients who dropped out early, but had a death date available per the national death registry, this date will be used in the calculation of days (and will be counted as an event). If a patient does not have an event or an early withdrawal date then days from randomization will be set to 30 days if their last follow-up date is known to occur after 30 days. These KM estimates will be put into the Z statistic defined in Section 2.3.1 using a margin of 2% to test for non-inferiority.
- Composite measure of all-cause mortality, MI, stroke (mRS≥1 and increase by ≥1 from baseline), or unplanned revascularization for ischemia occurring from the time of randomization up to study day 1095, as estimated by the Kaplan-Meier failure rate and analyzed using a Z statistic in the same way it is described under the Section 2.3.1, with a 1-sided alpha of 0.05 and a margin of 8.4%. All available data through 3-years of follow-up will be used. Days from the randomization date or the procedure date to the first occurrence of one of the events within this composite, an early withdrawal date, or the last follow-up date occurring by 3 years post randomization will be calculated for each patient. For patients

who dropped out early, but had a death date available per the national death registry, this date will be used in the calculation of days and counted as an event. If a patient does not have an event or an early withdrawal date:

- Days from randomization will be set to 1095 days (3 years) if their last follow-up date is known to occur after 3 years.
- The date of the last visit will be the date of the phone call, office visit or last medical contact.

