2.3.1 Primary Endpoint

The primary endpoint is the composite measure of all-cause death, myocardial infarction (MI) or stroke (modified Rankin Scale (mRS) ≥ 1 and increase by ≥ 1 from baseline). measured by the Kaplan-Meier failure rate estimate at 3 years. For the primary analysis of the primary endpoint, this Kaplan-Meier rate will be defined from the date of randomization. All available data through 3-year follow-up will be used, but only events occurring up to day 1095 after randomization will be counted for the primary endpoint. For a sensitivity analysis, the Kaplan-Meier rate will be defined at the time of the index procedure date. Both of these analyses will be conducted at the time when approximately 50% of the patients have reached the 3-year follow-up AND all patients have reached the 2-year follow-up, whichever time point is latest.

For the primary and sensitivity analyses, days from the randomization date and procedure date to the first occurrence of one of the events within this composite, an early withdrawal date, or the last follow-up date will be calculated for each patient respectively. For patients who dropped out early, but had a death date available per the national death registry, this date will be used in the calculation of days (and will be counted as a primary endpoint event). If a patient does not have an event or an early withdrawal date:

- Days from randomization will be set to 1095 days (3 years) if their last follow-up date is known to occur after 3 years.
- The date of the last visit will be the date of the last phone call, office visit or medical contact.

The primary endpoint will first be tested for noninferiority with a margin of 4.2%. The critical value will be generated using the Com-Nougue¹ approach to estimating the Z-statistic with Greenwood's formula for estimating the standard error.

$$Z = \frac{F_{CABG}(T) - F_{PCI}(T) - \delta}{\sqrt{Var(F_{CABG}(T)) + Var(F_{PCI}(T))}}$$

Where, for each treatment group (CABG or PCI):

F(T) = Kaplan Meier estimator of failure at time T

 δ = non-inferiority margin

Var = variance of the estimator = σ^2 , where σ is defined as:

$$\sigma$$
 = standard error by Greenwood's formula = S(T=1095) $\sqrt{\sum_{j=1}^{1095} \frac{d_j}{n_j s_j}}$

S = 1 - F = KM estimate of survival at time T

n = number of subjects

d = number of events

s = n-d

The 95% CI for $F_{CABG}(T) - F_{PCI}(T)$ is then:

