$$F_{CABG}(T) - F_{PCI}(T) \pm \mathbf{z}_{1-\alpha} \sqrt{Var(F_{CABG}(T)) + Var(F_{PCI}(T))}$$

P-value = 1- probnorm(Z)

Superiority testing of the primary endpoint will be performed using the same Z-statistic calculation that is defined above, without the non-inferiority margin. Statistical significance will be evaluated for both analyses at a 1-sided alpha level of 0.025.

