A sample size of 1,900 subjects (950 per arm) will provide approximately 99% power to demonstrate non-inferiority of PCI to CABG using the Z statistic from the Com-Nougue approach¹, which is similar to the normal approximation to the Binomial.

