3.3 Analysis of the Powered Secondary Endpoints

- The first powered secondary endpoints, the KM estimate of the composite rate of allcause mortality, MI or stroke (mRS≥1 and increase by ≥1 from baseline) from randomization to 30 days post randomization, will be analyzed in a similar fashion as the primary analysis of the primary endpoint described in Section 3.2 above. The key differences are that a 1-sided alpha is set at 0.05 and only non-inferiority will be tested at a margin of 2%.
- The second powered secondary endpoint is the KM estimate of the composite rate of all cause mortality, MI, stroke (mRS≥1 and increase by ≥1 from baseline) or unplanned revascularization at 3 years. The same analysis will be performed as described for the primary anaylsis of the primary endpoint except the non-inferiority margin = 8.4%

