3.10 MULTIPLICITY ISSUES

If EXCEL has met the primary analyses of its primary endpoint of the non-inferiority test on the ITT population, additional hypothesis tests for the of the powered secondary endpoints based on the ITT population will be performed following a fixed sequence as below (FWER=family wise error rate). All of these analyses will be performed from time from randomization:

Step 1: Family 1. Primary Endpoint: Death/MI/Stroke at 3 Years PCI non-inferior to CABG (one-sided alpha of 0.025) If passed non-inferiority, PROCEED to Step 2
If failed non-inferiority, STOP

Step 2: Family 2. Major Secondary Endpoint 1: Death/MI/Stroke at 30 Days PCI non-inferior to CABG

(one-sided alpha of 0.05)

If passed non-inferiority, PROCEED to Step 3
If failed non-inferiority, STOP

Step 3: (Simultaneous Testing of 3-1 and 3-2) 3-1. Family 1. Primary Endpoint: Death/MI/Stroke at 3 Years PCI superior to CABG (one-sided alpha of 0.025) 3-2. Family 3. Major Secondary Endpoint 2: Death/MI/Stroke/Revascularization at 3 Years PCI non-inferior to CABG

(one-sided alpha of 0.05)

For hypothesis test(s) of each of the major powered secondary endpoints, the type I error is a 1sided alpha of 0.05. If any hypothesis testing fails in steps 1 and 2, no further testing for the following step will be performed for labeling purposes. However they will still be tested for research and publication purposes. For example, if PCI failed to show non-inferiority to CABG for the major power secondary endpoint of Death/MI/Stroke at 30 Days (step 2), then the hypothesis in step 3 will not be tested for labeling purposes, but may be tested for exploratory reasons. Caution must be exercised when interpreting p-values displayed for analyses other than those performed for the primary and key powered secondary endpoints, as the study was not powered to detect differences on any of those other variables. The resulting p-values, whether or not less-than 0.05, may be a result simply due to chance, and are displayed for hypothesisgenerating purposes only.

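### The interval formula in SAP 2.3.1 gives 95% coverage only at one-sided alpha 0.025; reused at 0.05 for the two powered secondaries it yields a two-sided 90% interval that could be reported as 95%

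*SAP*

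**What the plan says.** **Formula.** SAP 2.3.1, on the primary endpoint, introduces the interval with "The 95% CI for $F_{CABG}(T) - F_{PCI}(T)$ is then" and prints the difference plus or minus z(1-alpha) times the standard error of the difference. The same section sets the level: "Statistical significance will be evaluated for both analyses at a 1-sided alpha level of 0.025".

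**Reuse.** SAP 2.3.2 puts the 30-day Kaplan-Meier estimates into the Z statistic of 2.3.1. It treats the 3-year composite that includes revascularization "in the same way it is described under the Section 2.3.1, with a 1-sided alpha of 0.05 and a margin of 8.4" per cent. SAP 3.3 says the 30-day endpoint is handled much like the primary and adds: "The key differences are that a 1-sided alpha is set at 0.05 and only non-inferiority will be tested at a margin of 2" per cent. For the 3-year secondary, SAP 3.3 says: "The same analysis will be performed as described for the primary anaylsis of the primary endpoint except the non-inferiority margin = 8.4" per cent. It does not restate alpha there.

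**Alpha elsewhere.** SAP 2.5.2 lists one-sided 0.05 for both secondaries, as does protocol 9.1.6.2. SAP 3.10 says: "For hypothesis test(s) of each of the major powered secondary endpoints, the type I error is a 1sided alpha of 0.05".

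**Decision rule.** SAP 3.4.4 declares non-inferiority when the upper limit of the one-sided (1-alpha) interval lies below the margin.

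**Other promised intervals.** SAP 3.5 promises 95% confidence intervals for differences in 3-year Kaplan-Meier estimates by subgroup, covering the primary and the major powered secondary endpoints. Where the SAP defines other two-sided intervals (3.4.1 for means, 3.4.2 for proportions), it uses alpha/2.

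**The concern.** The label in 2.3.1 is a fixed 95%, but the multiplier beneath it moves with alpha. The two agree only when one-sided alpha is 0.025. For both powered secondaries alpha is 0.05, and 2.3.1 holds the SAP's only formula for an interval on a Kaplan-Meier difference. A programmer who follows the cross-references could produce a 90% interval and print it under a 95% heading.

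What is at stake is the reported precision of two endpoints that SAP 3.10 ties to labelling, and of their subgroup displays. A reader could be shown a supposed 95% interval that excludes the margin when a real two-sided 95% interval would include it. Separately, SAP 3.3 leaves it unclear which alpha, and so which multiplier, applies to the 3-year secondary.

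**Working it through.** **Inputs (SAP 2.5.2).** 950 per arm. 30 days: 3% per arm, margin 2 points, one-sided alpha 0.05. 3 years: 22% per arm, margin 8.4 points, one-sided alpha 0.05, 8% loss, so 950 x 0.92 = 874 per arm. Differences are PCI minus CABG, as in the SAP's hypotheses. SAP 2.3.1 prints them the other way round, which does not affect a half-width.

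**1. Reproduce the plan's power.** SE = sqrt(2p(1-p)/n); power = Phi(margin/SE - z(1-alpha)).

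- 30 days: SE = sqrt(2 x 0.03 x 0.97/950) = 0.783 points. Power = Phi(2/0.783 - 1.645) = 81.9%, against about 80% stated. At alpha 0.025 it would be 72.4%, so the stated figure fits 0.05 only.
- 3 years: SE = sqrt(2 x 0.22 x 0.78/874) = 1.982 points. Power = Phi(8.4/1.982 - 1.645) = 99.5%. A Greenwood SE of 2.047 points (29-month accrual, 24-month minimum follow-up, exponential event and loss times assumed) gives 99.3%. The SAP states "approximately 99% power to demonstrate non-inferiority of PCI to CABG using the Z statistic". At alpha 0.025 the values are 98.9% and 98.4%, so this figure cannot show which alpha was meant.

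**2. Coverage of the printed formula.** Two-sided coverage = 2 x Phi(z(1-alpha)) - 1 = 1 - 2 x alpha.

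- Alpha 0.025: z = 1.960, coverage 95%.
- Alpha 0.05: z = 1.645, coverage 90%. The upper limit alone is a one-sided 95% bound.

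**3. Size of the shortfall.** 1.645/1.960 = 0.84, so the half-width is 16% too short whatever the SE, and therefore in any subgroup as well.

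| Endpoint | SE (points) | 1.645 x SE | 1.960 x SE |
|---|---|---|---|
| 30 days | 0.783 | 1.29 | 1.53 |
| 3 years, binomial | 1.982 | 3.26 | 3.88 |
| 3 years, Greenwood | 2.047 | 3.37 | 4.01 |

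**4. Where the two intervals differ about the margin.** This happens when the observed PCI excess lies between margin - 1.960 x SE and margin - 1.645 x SE.

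- 30 days: 0.47 to 0.71 points.
- 3 years: 4.52 to 5.14 points (4.39 to 5.03 with the Greenwood SE).

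With equal true rates, the chance of landing there is about 9.5% at 30 days and 0.7 to 0.9% at 3 years. When the true excess equals the margin, it is 2.5% for either endpoint.

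**5. Does the test change?** No. The limit that SAP 3.4.4 compares with the margin is the one-sided (1-alpha) bound, which at alpha 0.05 uses 1.645. The gap in step 4 is simply the difference between one-sided 0.05 and 0.025.

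**The case against.** The strongest reply is that the SAP never prints the error. The 95% label stands only over the primary endpoint, where it is correct. SAP 2.3.2 carries over the Z statistic and shows no interval for either secondary. The multiplier 1.645 is exactly what SAP 3.4.4 requires for a one-sided 0.05 test, so a two-sided 95% interval that includes the margin when the bound excludes it contradicts nothing.

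Most of this stands. It is why the point concerns labelling and reporting, and why the mislabelling is something that could happen, not something already on the page. It does not dispose of the point. SAP 3.5 does promise 95% intervals for Kaplan-Meier differences on these endpoints, and the SAP offers no formula for them except the one in 2.3.1.

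A reader might also infer that the plan needs a rule for reporting PCI as worse when the margin is met, or that the 3-year secondary should move to one-sided 0.025. The documents do not support either as a consequence of this formula. An outcome that is both non-inferior and significantly worse can arise whenever the margin is wide relative to the SE. Under the plan's equal 22% rates its chance is about 2%. It would not be hidden, since SAP 3.2 calls for hazard ratios, their intervals and p-values in time-to-event tables, and SAP 2.3.3 reports ischemia-driven revascularization separately. The 0.05 level is a pre-specified choice, and changing it would not correct the label.

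**Conclusion.** The concern holds as a specification gap in the SAP. Read literally, the 2.3.1 formula at alpha 0.05 produces two-sided 90% intervals, 16% too short, that could be issued as 95% for two powered secondaries and their subgroups. The 16% depends only on the two multipliers; the widths in points assume the design event rates and the stated loss and follow-up.

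A reader might infer that the secondary non-inferiority tests run at the wrong level. They do not. The bound in SAP 3.4.4 is valid, and with alpha 0.05, as stated in SAP 2.3.2 (3-year endpoint), 2.5.2 and 3.10, no decision, type I error or power figure changes.

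The one loose end that touches the test is SAP 3.3. Its exception for the margin alone leaves the 3-year secondary at 0.025 if taken literally, against 0.05 in SAP 2.3.2, 2.5.2 and 3.10 and in protocol 9.1.6.2. The stated power cannot settle which was meant, so the text must.

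**What to change.** 1. In SAP 2.3.1, write z(0.975) for every interval labelled two-sided 95%, and say that this applies to the primary, both powered secondaries and the subgroup differences in SAP 3.5.
2. For the two secondaries, call the z(0.95) limit used in the test a one-sided 95% bound, and note that it equals the upper limit of a two-sided 90% interval. Keep it as the decision limit; the two-sided 95% interval is for reporting only. Judging the 30-day endpoint on that interval would cut power from 81.9% to 72.4% and would need 1,143 per arm for 80%, against 900 at alpha 0.05.
3. In SAP 3.3, state alpha for the 3-year secondary so that it agrees with SAP 2.3.2, 2.5.2 and 3.10.

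The cost is a few lines of SAP text and the matching program code. No patients, power or pre-specified error rate are affected.

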2.3.3 Other Secondary Endpoints

The following additional endpoints will be analyzed:

- The endpoint of all-cause death, myocardial infarction or stroke, in-hospital, at 30 days, 180 days, and at 1, 2, 4 and 5 years.
- The endpoint of all-cause death, myocardial infarction, stroke or unplanned revascularization for ischemia in-hospital, at 30 days, 180 days, and 1, 2, 4 and 5 years.
- All cause mortality, cardiac death and non-cardiac death in-hospital, at 30 days, 180 days, and 1, 2, 3, 4 and 5 years.
- Protocol-defined MI at 30 days, 180 days, and 1, 2, 3, 4 and 5 years.
- All MI (periprocedural, spontaneous, Q-wave, and non Q-wave) at 30 days, 180 days, and 1, 2, 3, 4 and 5 years.
- MI adjudicated per Universal MI definition at 30 days, 180 days, and 1, 2, 3, 4 and 5 years.
- Protocol-defined stroke at 30 days, 180 days, and 1, 2, 3, 4 and 5 years.
- All stroke, ischemic stroke, and hemorrhagic stroke in-hospital, at 30 days, 180 days, and 1, 2, 3, 4 and 5 years.
- Disability following stroke event at 90 days± 2 weeks
- Complete revascularization at baseline procedure, anatomic and functional
- Ischemia-driven revascularization in-hospital, at 30 days, 180 days, and 1, 2, 3, 4 and 5 years.
 - All Ischemia-driven repeat revascularization procedures.
 - Ischemia-driven target lesion revascularization (TLR)
 - Ischemia-driven target vessel revascularization (TVR)
 - Ischemia-driven non target vessel revascularization (Non-TVR)

- All revascularization (ischemia driven and non-ischemia driven) at index procedure, in-hospital, at 30 days, 180 days, and 1, 2, 3, 4 and 5 years.
 - All repeat revascularization procedures
 - o All TLR
 - o All TVR
 - All non-TVR
- Stent thrombosis (ARC definition) symptomatic or asymptomatic PCI arm only inhospital, at 30 days, 180 days, and 1, 2, 3, 4 and 5 years.
- Symptomatic graft stenosis or occlusion (since this requires angiographic documentation, this endpoint will be compared to symptomatic ARC definite stent thrombosis) CABG arm only in-hospital, at 30 days, 180 days, and 1, 2, 3, 4 and 5 years.
- Bleeding complications at 30 days, 180 days, and 1, 2, 3, 4 and 5 years.
 - Requirement for blood product transfusion
 - TIMI scale (major or minor)
 - BARC scale
- Time from randomization to procedure; time from index procedure to discharge; ICU days; time from index procedure to return to work
- Major adverse events (MAE) defined as composite of the following components. MAE will be assessed in-hospital and at 30 days only.
 - o death
 - myocardial infarction
 - o stroke
 - \circ transfusion of ≥ 2 units of blood
 - TIMI major or minor bleeding
 - o major arrhythmia
 - o unplanned coronary revascularization for ischemia
 - any unplanned surgery or therapeutic radiologic procedure
 - o renal failure
 - o sternal wound dehiscence
 - o infection requiring antibiotics for treatment
 - \circ intubation for > 48 hours
 - o post-pericardiotomy syndrome.

2.3.4 Quality of Life

Quality of Life and Health Economics will be conducted during the trial. Analyses of these data will be described and conducted elsewhere.

2.4 ANALYSIS POPULATIONS

Hypothesis testing for the primary endpoint and the major powered secondary endpoints will be performed based on the Intent-to-Treat (ITT), As treated and Per-protocol (PP) populations. Primary analysis will be based on ITT. Other endpoint analyses, including the Economic Outcomes and Cost-Effectiveness Analysis will also be performed on both the ITT and PP populations. AEs collected for safety will only be summarized for the ITT population.

If there is any disagreement between the analysis results of the primary endpoint based on the three populations, potential causes for the disagreement will be investigated by careful examination of the clinical data. Information to be examined will include, but not be limited to, the number of enrolled subjects who did not meet all inclusion/exclusion criteria, the number of subjects and the justification for those who received a different treatment than that assigned by randomization, delays in receiving treatment, and the number of subjects lost to follow-up, by randomized treatment group.

2.4.1 Intent-to-Treat Population

The ITT population will consist of all subjects randomized in the study, regardless of the treatment actually received. Subjects will be analyzed in the treatment group to which they were randomized, regardless of actual treatment received.

2.4.2 Per-Protocol Population

The PP population consists of subjects with the following characteristics:

- received the initial treatment to which they were randomized
- assigned treatment must have been their first revascularization
- procedure performed within 4 weeks of randomization
- no violation of any inclusion-exclusion criteria

2.4.3 As-Treated Population

The as-treated population consists of subjects with the following characteristics:

• subjects who received a protocol defined treatment

Subjects will be included in the treatment arm corresponding to the first study treatment actually received.

2.5 SAMPLE SIZE CALCULATIONS

Calculations were performed to determine the minimum sample size required for this study in order to provide approximately 80% power for demonstrating non-inferiority of the primary endpoint. The assumed true event rates used in the calculations of all powered endpoints were estimated based on the SYNTAX² trial and on results from previous studies of the XIENCE V® stent. All powered non-inferiority endpoints will be analyzed using the Com-Nougue approach¹, using Kaplan-Meier estimates calculated from time from randomization.

2.5.1 Primary Endpoint

The primary endpoint of all cause death, MI or stroke (mRS \geq 1 and increase by \geq 1 from baseline) occurring up to 3 years post randomization will be evaluated using the difference in Kaplan-Meier failure rates in the intent-to-treat population. For the primary endpoint, sample size calculations for the Com-Nougue approach¹, which utilizes the difference in Kaplan-Meier failure rate estimates, were derived using simulations. The Com-Nougue approach was very similar to that calculated using the asymptotic approach (difference \leq 0.5%). Therefore, the asymptotic test was used to approximate the power for the Com-Nougue approach using PASS 2008 (NCSS, LLC. Kaysville, Utah)³.

The hypothesis test is designed to show non-inferiority of PCI to CABG for the primary endpoint via the Z statistic, which is a normal approximation to the Binomial, with a one-sided alpha of 0.025. The null (H_0) and alternative (H_A) hypotheses are:

```
H0: F_{PCI-PE}(T) - F_{CABG-PE}(T) \ge \Delta_{PE}
```

```
HA: F_{PCI-PE}(T) - F_{CABG-PE}(T) < \Delta_{PE}.
```

 F_{PCI-PE} and $F_{CABG-PE}$ are the Kaplan-Meier estimates of failure rate of the primary endpoint at 3 years in the PCI and CABG arms, respectively. Δ_{PE} is the non-inferiority margin for the primary endpoint.

The sample size calculation is based on the following assumptions:

- primary endpoint event rate is 11% in each treatment arm at 3 years (using 3-year event rates from the SYNTAX trial, the most contemporary reference dataset)
- minimum time to follow-up is 2 years
- median time to follow-up is approximately 3 years
- 8% lost to follow-up at 3 years
- non-inferiority margin $\Delta_{\text{PE}} = 4.2\%$
- one-sided alpha = 0.025
- accrual time of 29 months.

A sample size of 1,900 subjects (950 per arm) will provide approximately 80% power to

demonstrate non-inferiority of PCI to CABG.

If non-inferiority is met, superiority testing will be performed with a one-sided alpha of 0.025. The null (H_0) and alternative (H_A) hypotheses for the superiority test are:

H₀: $F_{PCI-PE}(T) - F_{CABG-PE}(T) \ge 0$

H_A: $F_{PCI-PE}(T) - F_{CABG-PE}(T) < 0$.

Using a one-sided alpha of 0.025, assuming 8% lost to follow-up at 3 years, the trial will have approximately 80% power to demonstrate superiority with a difference of 3.84% of PCI to CABG (e.g. 7.16% in the PCI arm vs. 11% in the CABG arm).

2.5.2 Major Powered Secondary Endpoints:

The first major powered secondary endpoint is defined as the composite of all cause death, MI, or stroke (mRS \geq 1 and increase by \geq 1 from baseline) occurring up to 30 days post randomization. It will be evaluated using the difference in Kaplan-Meier rates tested using the Com-Nougue approach¹ which is similar to the normal approximation to the binomial. The null (H₀) and alternative (H_A) hypotheses for non-inferiority of this major secondary endpoint is:

H₀: $F_{PCI-PE30}(T) - F_{CABG-PE30}(T) \ge \Delta_{PE30}$

H_A: $F_{PCI-PE30}(T) - F_{CABG-PE30}(T) < \Delta_{PE30.}$

 $F_{PCI-PE30}(T)$ - $F_{CABG-PE30}(T)$ is the difference in Kaplan-Meier rates at 30 days between PCI and CABG arms and Δ_{PE30} is the non-inferiority margin for this powered secondary endpoint.

The power calculation is based on the following assumptions:

- composite event rate is 3% in each treatment arm at 30 days
- non-inferiority margin $\Delta_{\text{PE30}} = 2\%$
- one-sided alpha = 0.05

A sample size of 1,900 subjects (950 per arm) will provide approximately 80% power to demonstrate non-inferiority of PCI to CABG.

The second major powered secondary endpoint is defined as the composite of all cause death, MI, stroke, or unplanned revascularization for ischemia occurring by 3 years post randomization. This composite will be evaluated using the difference in Kaplan-Meier failure rates at 3 years between CABG and PCI in all 3 patient populations. The hypothesis is designed to show non-inferiority of PCI to CABG with a one-sided alpha of 0.05. The null (H₀) and alternative (H_A) hypotheses for non-inferiority of this powered secondary endpoint are:

H₀: $F_{COMP-PCI}(T) - F_{COMP-CABG}(T) \ge \Delta_{COMP}$ H_A: $F_{COMP-PCI}(T) - F_{COMP-CABG}(T) < \Delta_{COMP}$. $F_{COMP-PCI}(T) - F_{COMP-CABG}(T)$ is the difference in failure rates at 3 years between CABG and PCI and Δ_{COMP} is the non-inferiority margin for this powered secondary endpoint.

The power calculation is based on the following assumptions:

- composite event rate is 22% in each treatment arm at 3 years
- minimum time to follow-up is 2 years
- median time to follow-up is approximately 3 years
- 8% lost to follow-up at 3 years
- non-inferiority margin $\Delta_{\text{COMP}} = 8.4\%$
- one-sided alpha = 0.05
- accrual time of 29 months

A sample size of 1,900 subjects (950 per arm) will provide approximately 99% power to demonstrate non-inferiority of PCI to CABG using the Z statistic from the Com-Nougue approach¹, which is similar to the normal approximation to the Binomial.

